## 6 STATISTICAL METHODS

In general, continuous variables will be summarized using descriptive statistics such as mean, SD, median, first quartile (Q1), third quartile (Q3), and range (minimum and maximum). Categorical variables will be summarized using frequency and percentage. For time-to-event variables, the Kaplan-Meier (K-M) method will be used for descriptive summaries. For the calculation of time-to-event or duration-of-event variables, the difference between the start date and the end date plus 1 day will be used. For events (eg, baseline disease characteristics or prior therapies) prior to randomization, the durations will be calculated as the date of randomization minus the date of the event; the details are specified in [Section 9.4.1](#).

For any efficacy endpoint that involves complete response (CR) or partial response (PR), the endpoint will be calculated using the confirmed CR/PR, i.e., any CR or PR must be confirmed not less than 4 weeks following the initial achievement of the response.

## 6.1 Study Endpoints

Efficacy endpoints related to tumor assessments will be evaluated by IIR and investigator assessment during the randomization phase and investigator assessment only during the extension phase.

### 6.1.1 Primary Endpoint

Progression-free survival (PFS) by IIR is defined as the time from the date of randomization to the date of the first documentation of PD or death (whichever occurs first) as determined by IIR using RECIST 1.1.

### 6.1.2 Secondary Endpoints

1. Progression-free survival rate at 4 months (PFS-4m) by IIR is defined as the percentage of subjects who are alive and without PD at 4 months from the randomization date as determined by IIR of radiological imaging using RECIST 1.1. The PFS-4m rate is estimated using the Kaplan-Meier (K-M) method.
2. Progression-free survival rate at 1 year (PFS-1y rate) by IIR is defined as the percentage of subjects who are alive and without PD at 1 year from the randomization date as determined by IIR of radiological imaging using RECIST 1.1. The PFS-1y rate is estimated using the K-M method.
3. Overall survival (OS) is defined as the time from the date of randomization to the date of death from any cause. Subjects who are lost to follow-up and those who are alive at the date of data cutoff for the primary analysis, will be censored at the date the subject was last known to be alive, or date of data cutoff for the primary analysis, whichever occurs first. Overall survival rate at 1 year (OS-1y) will be estimated using the K-M method.
4. Objective response rate by IIR at 4 months (ORR-4m) is defined as the proportion of subjects who have best overall response of complete response (CR) or partial response (PR) as determined by IIR using RECIST 1.1 within the first 4 months.
5. Objective response rate (ORR) by IIR is defined as the proportion of subjects who have best overall response of CR or PR as determined by IIR using RECIST 1.1.
6. Safety will be assessed by summarizing the incidence of treatment-emergent adverse events (TEAEs) and SAEs together with all other safety parameters.
7. Assessment of population-based PK parameters of lenvatinib.
8. Score changes from baseline for all PedsQL scales including Generic Core Scales and Cancer Module. Scores will be calculated for total generic score, total cancer score, each physical function subscale including physical health, psychosocial health, emotional function, social function, school/work function in the Generic Core Scales, and each subscale in the cancer module.
9. Palatability and acceptability of the suspension formulation of lenvatinib in subjects receiving the suspension formulation in the study will be assessed by using the Palatability Questionnaire (see Appendix 4 of the Protocol).

### 6.1.3 Exploratory Endpoints

1. Duration of response (DOR) by IIR and investigator assessment is defined as the time from the date a response was first documented until the date of the first documentation of PD or date of death from any cause.
2. Disease control rate (DCR) by IIR and investigator is the proportion of subjects who have a best overall response of CR or PR or stable disease (SD). In this context, stable disease is defined as stable disease at  $\geq 5$  weeks after randomization to be considered best overall response.
3. Clinical benefit rate (CBR) by IIR and investigator is the proportion of subjects who have best overall response of CR or PR or durable SD (duration of SD  $\geq 23$  weeks after randomization).
4. Efficacy endpoints (PFS, PFS-4m, PFS-1y, ORR-4m, and ORR) evaluated based on investigator assessment.
5. Proportion of subjects who achieve complete removal of baseline lesions and the proportion of subjects with unresectable baseline lesions(s) that are converted to resectable between the 2 treatment arms.
6. Blood and tumor biomarkers will be assessed for identifying potential correlation with clinical outcomes-related endpoints.

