## 6.2 Study Subjects

### 6.2.1 Definitions of Analysis Sets

- The Full Analysis Set (Intent-to-Treat Analysis [ITT]) includes all randomized subjects regardless of the treatment actually received. This is the primary analysis population used for the efficacy analyses which will be based on the ITT principle.
- The Per Protocol Analysis Set includes those subjects from the ITT set who received at least 1 dose of any study drug, had no important protocol deviations, and had both baseline and at least one postbaseline tumor assessment. Subjects for whom death occurred prior to the first postbaseline tumor assessment will also be included. The per protocol analysis set will be the secondary analysis set for the primary efficacy endpoint.
- The Safety Analysis Set includes subjects who received at least 1 dose of any study drug. This is the analysis population used for all safety analyses which will be based on the as-treated principle.
- Population Pharmacokinetic (PK) Analysis Set includes the subjects who have received at least 1 dose of lenvatinib with documented dosing history and have measurable plasma levels of lenvatinib.
- The Pharmacodynamic Analysis Set includes subjects who received at least 1 dose of study drug and had sufficient pharmacodynamic data (eg, at least 1 evaluable/measurable pharmacodynamic parameter).
- The HRQoL Analysis Set will consist of all randomized subjects who have received at least 1 dose of study medication, and have completed at least 1 patient-reported outcome (PRO) assessment beyond baseline. For the analysis, subjects will be analyzed as randomized and not according to treatment actually received.

Analysis sets in data analyses are tabulated below.

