### 6.3.4 Examination of Subgroups

For the primary efficacy endpoint PFS as assessed by IIR, the median PFS, hazard ratio, and corresponding 95% confidence intervals may be generated for the following subgroups, as appropriate.

- Age ( $<18$  years,  $\geq 18$  years)
- Time to first relapse ( $<18$  months,  $\geq 18$  months)
- Sites of metastasis [Lung only, Others (+/- lung)]
- Prior Ifosfamide +/- Etoposide (Yes, No)
- Measurable disease [Yes (Subjects with at least 1 target lesion), No (Subjects with only non-target lesions)]

For the safety endpoints, the following TEAE tables will be provided by age group (years) category ( $<18$  years,  $\geq 18$  years) and gender.

- Overall summary of TEAE
- TEAEs in decreasing frequency of PT
- Serious TEAEs in decreasing frequency of PT

Other exploratory subgroup analyses may be conducted if appropriate.

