#### 6.4.2.3 Overall Response Rate (ORR) and ORR-4m by IIR

The ORR by IIR is the proportion of subjects with a best overall response of CR or PR determined by IIR using RECIST 1.1. The ORR by IIR will be summarized and compared between the two treatment arms. The raw difference in ORR will be reported. The 2-sided 95% confidence interval of ORR difference will be generated from SAS using Miettinen-Nurminen (Score) Confidence Limits.

The ORR-4m by IIR will be summarized and compared between arms using the same approach as for ORR by IIR.

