#### 6.4.2.4 Duration of Response, Disease Control Rate, and Clinical Benefit Rate by IIR

Median DOR by IIR among responders for each arm will be presented along with the corresponding 2-sided 95% CI; 95% CI will be estimated with the Brookmeyer and Crowley method.

Disease Control Rate (DCR) and CBR by IIR will be summarized and compared between arms using the same approach as for ORR.

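### DCR and CBR have no category for non-progression in subjects with only non-target lesions, so a literal reading understates both rates

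*SAP*

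**What the plan says.** SAP section 6.1.3, item 2, states that DCR by IIR and by investigator "is the proportion of subjects who have a best overall response of CR or PR or stable disease (SD". It then adds a time condition: "In this context, stable disease is defined as stable disease at" 5 weeks or more after randomization. Item 3 states that CBR "is the proportion of subjects who have best overall response of CR or PR or durable SD", where durable means at least 23 weeks after randomization. Both definitions are closed lists.

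The SAP also foresees randomized subjects without target lesions. The baseline characteristics in section 6.2.4 and the PFS subgroups in section 6.3.4 both carry a measurable-disease level worded "No (Subjects with only non-target lesions". No count is given.

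The denominator is not restricted to measurable disease. The Full Analysis Set "includes all randomized subjects regardless of the treatment actually received", and section 6.4 makes it the main set for efficacy. Section 6.4.2.4 says: "Disease Control Rate (DCR) and CBR by IIR will be summarized and compared between arms using the same approach as for ORR". Section 6.4.2.5 applies the same approach to the investigator's assessments. The response criteria are RECIST 1.1 (sections 4.1.1, 6.1.1 and 6.1.2).

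**The concern.** Under RECIST 1.1, PR and SD are judged on the sum of target-lesion diameters. A subject with no target lesion who has neither a complete response nor progression is classed as Non-CR/Non-PD. That term is absent from section 6.1.3, from the list of abbreviations and from the rest of the SAP.

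Taken at its word, the closed list keeps such a subject in the denominator and lets the subject into the numerator only through CR. Someone without progression for a year would then be a long progression-free survivor in the primary analysis but count as neither controlled nor benefiting here. Both rates would be too low, and the difference between arms would also be altered. Measurable disease is not a stratification factor (section 4.2), so nothing in the design ensures that these subjects split evenly.

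The version history suggests how the gap arose: version 3.0 added the measurable-disease subgroup and also revised the SD duration for DCR, without linking the two.

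**Working it through.** **The plan's own figure.** The SAP gives no expected rate, power or sample size for DCR or CBR, so there is none to reproduce for them. Its one sizing calculation (section 5) is 38 PFS events for a hazard ratio of 0.4, one-sided 0.025 and 80% power.
- Schoenfeld's formula with 1:1 allocation: 4 × (1.960 + 0.842)² / (ln 0.4)² = 4 × 7.849 / 0.8396 = 37.4, rounded up to 38. Power at 38 events is 0.806.
- The assumed medians agree with the hazard ratio: 3.5 / 8.75 = 0.40.

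This figure does not depend on how DCR or CBR is defined.

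**Inputs for the size of the problem.**
- From section 5: median PFS of 8.75 months (Arm A) and 3.5 months (Arm B). At 4.348 weeks per month these are 38.05 and 15.22 weeks.
- From sections 6.3.2 and 8: 81 subjects in the ITT population, hence about 40 per arm.
- Assumed, because the SAP is silent: a share s of 5% to 20% with only non-target lesions (about 4 to 16 of 81); exponential PFS, equal for subjects with and without target lesions; no CR among the non-target-only subjects; Non-CR/Non-PD not counted.

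**Proportion free of progression at time t:** S(t) = 0.5^(t / median).
- Week 6, the first scheduled scan, for DCR: Arm A 0.5^(6/38.05) = 0.896; Arm B 0.5^(6/15.22) = 0.761.
- Week 23, for CBR: Arm A 0.5^(23/38.05) = 0.658; Arm B 0.5^(23/15.22) = 0.351.

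**Understatement of each rate = s × S(t), in percentage points.**

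| | s = 5% | s = 20% |
|---|---|---|
| DCR, Arm A | 4.5 | 17.9 |
| DCR, Arm B | 3.8 | 15.2 |
| CBR, Arm A | 3.3 | 13.2 |
| CBR, Arm B | 1.8 | 7.0 |

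DCR is therefore understated by about 4 to 18 points.

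**Equal shares in both arms.** The difference between arms shrinks by s × (S_A − S_B).
- DCR: 0.05 × 0.136 = 0.7 points to 0.20 × 0.136 = 2.7 points.
- CBR: 0.05 × 0.307 = 1.5 points to 0.20 × 0.307 = 6.1 points.

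**Unequal shares, DCR, 10 such subjects in total.**
- 7 in A, 3 in B: A loses 7/40 × 0.896 = 15.7 and B loses 3/40 × 0.761 = 5.7. The difference A − B falls by 10.0 points.
- 3 in A, 7 in B: A loses 6.7 and B loses 13.3. The difference rises by 6.6 points.
- 5 in each: A loses 11.2 and B loses 9.5. The difference falls by 1.7 points.

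The net shift under a 7:3 split is thus about 7 to 10 points. Measured from the even split, imbalance alone contributes 8.3 points in either direction (10.0 − 1.7 and 6.6 + 1.7).

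**The case against.** The strongest reply is that the SAP never says these subjects count as failures. A reader might infer that they are certain to be scored so, but the document does not establish it. Section 10 places the derivation rules and dataset specifications in separate documents, and the SAP's abbreviations cover only CR, PR, SD, PD and NE. If those specifications, the protocol or the imaging rules record non-progression without target lesions as SD, nothing is lost. The Non-CR/Non-PD label itself comes from RECIST 1.1, which the SAP cites but does not reproduce. This part of the reply stands. What remains is that the SAP's list is closed and no mapping is stated, so two programmers could derive different rates from the same data.

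The reply on size also stands. The number of non-target-only subjects is unknown. With none the effect is nil, and with one it is at most 1/40, or 2.5 points, in one arm. Any CR among them reduces it further.

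Two other stronger readings are not supported. A reader might infer that ORR and ORR-4m are wrong because the same subjects are in their denominators. The definition is "The ORR by IIR is the proportion of subjects with a best overall response of CR or PR determined by IIR using RECIST 1.1", and keeping all randomized subjects in the denominator follows the stated ITT principle. That is a legitimate choice, not an error. A reader might also infer that DCR and CBR would invalidate PFS. They would sit oddly beside it for the same subjects, but PFS is a time-to-event endpoint that does not use these categories.

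**Conclusion.** The point holds as a gap in two exploratory definitions. Section 6.1.3 lists only CR, PR and SD, the SAP foresees subjects who under RECIST 1.1 may have none of these while not progressing, and no restriction of the denominator compensates. Followed literally, DCR and CBR are understated by roughly the share of such subjects times their non-progression rate.

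The DCR range of 4 to 18 points, and the net shift of about 7 to 10 points in the arm difference under a 7:3 split of 10 subjects, are illustrations. They rest on the SAP's assumed medians and on a share and split that the SAP does not give. The direction of any bias in the arm difference cannot be known without the actual split.

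Severity is minor. No sample-size or multiplicity provision depends on DCR or CBR, and the primary PFS analysis is untouched.

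**What to change.** In section 6.1.3, for both IIR and investigator assessment:
- define DCR as a best overall response of CR, PR, SD or Non-CR/Non-PD, with SD or Non-CR/Non-PD at 5 weeks or more after randomization;
- define CBR as CR, PR, or SD or Non-CR/Non-PD lasting at least 23 weeks after randomization.

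Add Non-CR/Non-PD to the abbreviations and show it as its own row in the best-overall-response table. If the dataset specifications already map it to SD, say so in section 6.1.3 instead.

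Optionally, add supportive ORR and ORR-4m tables in subjects with at least one target lesion, leaving the Full Analysis Set versions as they are. The flag is already needed for the section 6.3.4 subgroup.

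The cost is a few lines of SAP text, one response category in the derivation and, if wanted, two tables. No new data are needed.

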## 6.2 Study Subjects

### 6.2.1 Definitions of Analysis Sets

- The Full Analysis Set (Intent-to-Treat Analysis [ITT]) includes all randomized subjects regardless of the treatment actually received. This is the primary analysis population used for the efficacy analyses which will be based on the ITT principle.
- The Per Protocol Analysis Set includes those subjects from the ITT set who received at least 1 dose of any study drug, had no important protocol deviations, and had both baseline and at least one postbaseline tumor assessment. Subjects for whom death occurred prior to the first postbaseline tumor assessment will also be included. The per protocol analysis set will be the secondary analysis set for the primary efficacy endpoint.
- The Safety Analysis Set includes subjects who received at least 1 dose of any study drug. This is the analysis population used for all safety analyses which will be based on the as-treated principle.
- Population Pharmacokinetic (PK) Analysis Set includes the subjects who have received at least 1 dose of lenvatinib with documented dosing history and have measurable plasma levels of lenvatinib.
- The Pharmacodynamic Analysis Set includes subjects who received at least 1 dose of study drug and had sufficient pharmacodynamic data (eg, at least 1 evaluable/measurable pharmacodynamic parameter).
- The HRQoL Analysis Set will consist of all randomized subjects who have received at least 1 dose of study medication, and have completed at least 1 patient-reported outcome (PRO) assessment beyond baseline. For the analysis, subjects will be analyzed as randomized and not according to treatment actually received.

Analysis sets in data analyses are tabulated below.

**Table 1 Analysis Sets in Data Analysis**

| Tables  | All Screened Subjects | Full Analysis Set | Per-Protocol Analysis Set | Safety Analysis Set | PK Analysis Set | PD Analysis Set | HRQoL Analysis Set |
|---|-----------------------|-------------------|---------------------------|---------------------|-----------------|-----------------|--------------------|
| Protocol Deviations   |                       | •                 |                           |                     |                 |                 |                    |
| Disposition   | •                     | •                 |                           |                     |                 |                 |                    |
| Demography & Baseline Characteristics   |                       | •                 |                           |                     |                 |                 |                    |
| Disease History   |                       | •                 |                           |                     |                 |                 |                    |
| Prior and concomitant medication  |                       | •                 |                           |                     |                 |                 |                    |
| New anticancer therapy  |                       | •                 |                           |                     |                 |                 |                    |
| Efficacy analysis   |                       | •                 | •                         |                     |                 |                 |                    |
| Safety analysis (including drug exposure, AEs, laboratory tests, vital signs, etc.) |                       |                   |                           | •                   |                 |                 |                    |
| Pharmacokinetics  |                       |                   |                           |                     | •               |                 |                    |
| Pharmacodynamics  |                       |                   |                           |                     |                 | •               |                    |
| HRQoL   |                       |                   |                           |                     |                 |                 | •                  |

AEs = adverse events, HRQoL = Health-Related Quality of Life, PD = pharmacodynamic, PK = pharmacokinetic.

### 6.2.2 Subject Disposition

All subjects who were screened for the study will be reported. The number of subjects who failed screening and the reasons for screen failures will be summarized.

The summary of subject disposition will be conducted on the Full Analysis Set.

The number of subjects who were randomized, treated, discontinued study treatment, and the reasons for discontinuation of study treatment will be summarized.

The end of study status (Alive, Death, Withdrew Consent, Lost to Follow-up, etc.) at the data cutoff date will also be summarized by treatment arm and overall.

### 6.2.3 Protocol Deviations

Protocol deviations will be identified and documented prior to database lock.

Important protocol deviations will be appropriately grouped into different categories. They will be summarized by treatment arm within the Full Analysis Set if necessary. A list of subjects with important protocol deviations will be provided.

In addition, a listing of all protocol deviations due to COVID-19 will be provided.

### 6.2.4 Demographic and Other Baseline Characteristics

Demographic and baseline characteristics will be summarized for the Full Analysis Set.

The following demographic and baseline characteristics will be summarized:

- Age (years)
- Age group ( $\geq 2$  years to  $< 6$  years,  $\geq 6$  years to  $< 17$  years [ $\geq 6$  years to  $< 12$  years,  $\geq 12$  years to  $< 17$  years],  $\geq 17$  years)
- Age group ( $\geq 2$  years to  $< 12$  years,  $\geq 12$  years to  $< 18$  years,  $\geq 18$  years)
- Age group from interactive response technology (IRT) ( $< 18$  and  $\geq 18$  years)
- Gender (Male, Female)
- Race (White, Black, Asian, American Indian or Alaska Native, Native Hawaiian or Other Pacific Islander, Other); Asian subcategories: Chinese, Japanese, Other.
- Race group (White, Non-White)
- Ethnicity (Hispanic or Latino, Not Hispanic or Latino)
- Region (North America, Europe, and Asia Pacific)
- Pregnancy test results (Positive, Negative) in females
- Tanner stage
- Height (cm)
- Baseline weight (kg)
- Baseline body mass index (BMI) ( $\text{kg}/\text{m}^2$ )
- Baseline body surface area (BSA) ( $\text{m}^2$ )
- Karnofsky performance status (KPS) or Lansky play scores (LPS)
- Strata will be summarized based on IRT and CRF data. Strata are defined by the two stratification factors of time to first relapse/refractory disease and age:
  - Early ( $< 18$  months) and age group ( $< 18$  years)
  - Early ( $< 18$  months) and age group ( $\geq 18$  years)
  - Late ( $\geq 18$  months) and age group ( $< 18$  years)
  - Late ( $\geq 18$  months) and age group ( $\geq 18$  years)

The following disease history and characteristics at study entry will also be summarized:

- Time since first diagnosis of osteosarcoma to randomization date (months)
- Time since metastatic diagnosis to randomization date (months)
- Time since last progression to randomization date (months)
- Age at diagnosis (in years)
- Osteosarcoma subtypes
- Location of the primary tumor
- TNM staging and grades
- Measurable disease [Yes (Subjects with at least 1 target lesion), No (Subjects with only non-target lesions)]
- Resectable Lesions at Baseline
- Sites of metastasis at baseline (bone, lung, bone AND lung, brain, liver, lymph, and other)

The following previous anticancer therapies/medications will also be summarized:

- Number of previous medication regimens
- Duration of most recent medication (months)
- Best response for most recent medication [complete response (CR), partial response (PR), stable disease (SD), progressive disease (PD), not evaluable (NE), not applicable (NA), unknown]
- Time from end of most recent medication to date of randomization (months)
- Therapeutic setting (Adjuvant, Maintenance, Neo-adjuvant, and Therapeutic)
- Previous radiotherapy (Yes, No)
  - Time from end of most recent radiotherapy to date of randomization (months)
  - Site of previous radiotherapy
  - Tumor lesion at the site progressed since most recent radiotherapy (Yes, No, Not evaluable)
- Previous anthracycline therapy (Yes, No)
- Previous receptor tyrosine kinase inhibitor (RTKI) therapy (Yes, No)
- Previous ifosfamide monotherapy (Yes, No)
- Previous ifosfamide plus etoposide (Yes, No)
- Previous Anticancer Procedures (Procedure Name; Site/Organ; Has tumor lesion at the site progressed since the procedure? (Yes, No); Post Op Result: Complete Resection, Incomplete Resection).

Demographic and baseline disease characteristics, prior anticancer therapies/medications will also be listed for each subject.

